## 4. STUDY DESIGN

### 4.1 Study Blinding

This is an open-label study.

### 4.2 Randomization to Treatment Groups

The treatments will be randomized to subject identification numbers by the IXRS® provider in a 2:1 fashion, i.e., 2  $\times$  cefiderocol and 1  $\times$  BAT. An interactive web or voice response system (IWRS/IVRS) will be used to assign subjects to identification numbers for which treatment has already been randomly assigned. Randomization will be performed by the stochastic minimization method using their infection site (HABP/VABP/HCABP, cUTI, and BSI/sepsis), APACHE II score ( $\leq$  15 and  $\geq$  16), and region (North America, South America, Europe, and Asia-Pacific) as allocation factors. To avoid deterministic allocation based on the ongoing allocation results, probabilistic allocation will be incorporated.

The population with HABP/VABP/HCABP will be approximately 50% of randomized subjects; cUTI is limited to no more than 30% of randomized subjects, and the remainder of subjects will be enrolled under the BSI/sepsis diagnosis. The randomization ratio of subjects between treatment groups based on clinical diagnosis will be maintained through the allocation factor of clinical diagnosis at the time of randomization. The process for

---

subject number assignment and treatment assignment is described in the study procedure manual.

#### **4.3 Sample Size**

Approximately 150 subjects will be randomized 2:1 (2 × cefiderocol and 1 × BAT) to each group. This sample size will ensure that approximately 100 subjects are treated with cefiderocol.

#### **4.4 Study Schematic**

The study design is shown in [Figure 4-1](#). The study time and events table is shown in [Appendix 1](#).

**Figure 4-1** **Study Schematic**

D -2 to D 1	D 1	D 3 (after 6 doses)	D 3 to D 4	Up to D 14 a	EOT + 7 (± 2)	EOT + 14 (± 3)	EOT + 28 (± 3)
Screening	Randomization	PK	Early Clinical/Micro Assessment (EA)	End of Treatment (EOT)	Test of Cure (TOC)	Follow-up (FU)	End of Study (EOS)

**Treatment Period**

Cefiderocol 2 g intravenous dosing  
at 8-hour intervalsb

BAT either polymyxin-based or  
nonpolymyxin-based

BAT = best available therapy; D = days; EA = Early Assessment; eCRF = electronic case report form; EOT = End of Treatment (last day of study treatment); PK = pharmacokinetics

Each day is a calendar date (i.e., D2 is the next day/date after D1 in calendar).

- a The treatment duration can be extended up to 21 days based on the investigator's clinical assessment of the subject. A clear reason should be documented in the eCRF.
- b Dosing adjustments for augmented renal clearance and renal impairment (see [Table 5-2](#) in protocol).

## 5. ANALYSIS POPULATIONS

The following analysis populations will be defined in this study.

### 5.1 Intent-to-treat Population

The Intent-to-treat population is defined as all randomized subjects who received at least 1 dose of the study treatment.

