## **7.13 Withdrawal or Discontinuation of Patients from the Study or Study Treatment**

The investigator will make every reasonable attempt to complete the study for each enrolled patient. A patient may withdraw consent to participate in the study for any reason at any time. The investigator will advise the sponsor about the withdrawal of any patient from the study by using the IWRS/IVRS.

The investigator or sub-investigator will discontinue a patient from the study treatment for any of the following reasons. Please note that unless the patient withdraws consent to participate in the study, all randomized patients should be followed for the entire duration of the study:

- A serious or intolerable AE occurs and the investigator considers that the patient should be withdrawn because of the AE.
- The target disease worsens because of poor response to the study treatment and the investigator considers that the patient should be withdrawn.
- The patient requests to be withdrawn from the study.
- The patient is lost to follow-up.
- The investigator determines that the patient should be withdrawn because of other reasons.

For patients who withdraw or are discontinued by the investigator or sub-investigator at any time after the start of treatment, they are still considered to be in the study, and they

should still be followed through to the completion of all study activities, ie, EOT, TOC, FUP, and EOS, if at all possible. All withdrawn or discontinued patients will remain in the study for safety and clinical outcome purposes.

All patients discontinued due to AEs will be followed until resolution of any AEs, until the unresolved AEs are judged by the investigator to have stabilized, or the patient is lost to follow-up.

Patients who withdraw or are discontinued from study treatment should receive additional standard of care antibiotic therapy if in the judgment of the investigator such treatment is clinically indicated (see Section 6.2.4).

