### 9.3 Analysis Populations

The following analysis populations will be examined in this study:

- Intent to Treat (ITT) population: All randomized patients who received at least 1 dose of the study treatment.
- Microbiological Intent to Treat Population (Micro-ITT): All ITT patients who have a baseline Gram-negative pathogen from an appropriate clinical specimen. Patients should not be excluded from this population based upon events that occurred post randomization (eg, loss to follow-up).
- Carbapenem-Resistant Microbiological Intent to Treat Population (CR Micro-ITT): All Micro-ITT patients whose baseline Gram-negative pathogen is carbapenem-resistant.

- Carbapenem-Resistant Microbiologically Evaluable Population (CR-ME): includes all CR Micro-ITT patients who follow important components of the study as specified in the protocol with no major protocol violations. Criteria for inclusion are:
  - $\geq 5$  days of intravenous (IV) study treatment unless treatment was a failure
  - Underwent TOC assessment
  - Patients without any major protocol inclusion or exclusion violations
  - Patients with no violations of restrictions for concomitant therapy including concomitant antibiotic(s) effective against Gram-negative bacteria
- Safety population includes all randomized patients who receive at least 1 actual dose of the study treatment (ITT population). The population will be analyzed according to the treatment that the patients actually received, rather than the treatment to which the patients were randomized.
- The PK concentration population includes all patients who undergo plasma sampling and have at least one evaluable PK assay result for S-649266. This population will be used for the concentration listing, plotting of the concentration-time data and the concentration summary.

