## **6.6 Study Day Definition**

Day 1 is the calendar day on which each subject takes initial investigational medicinal product (IMP). However, Day 1 is the calendar day of randomization for subjects who did not take any IMP. Previous day to Day 1 is expressed as Day -1, and days before Day -1 in Screening Period are expressed as Day -2, Day -3, ..., etc.

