## 7. DEMOGRAPHIC AND OTHER BASELINE CHARACTERISTICS

### 7.1 Subject Disposition and Discontinuation

Subject disposition will be summarized for the all screened subjects. The following subjects' disposition categories will be included:

- Subjects who were screened
- Subjects who were screen failed

For the subjects who were screen failed, they will be also summarized by respective reasons.

Subject disposition will be summarized by treatment group for the all randomized subjects. The following subjects' disposition categories will be included:

- Subjects who were randomized
- Subjects who were randomized and treated
- Subjects who completed treatment
- Subjects who did not complete treatment
- Subjects who completed the study
- Subjects who discontinued early from the study

Subjects who received study drug for 7 days or more (for cUTI subjects, 5 days or more) will be considered as subjects who completed treatment. Subjects who did not complete treatment and subjects who discontinued early from the study will be also summarized by respective reasons.

The number of subjects in the ITT population, Micro-ITT population, CR Micro-ITT population, CR-ME population, and Safety population will be obtained by treatment group. The reasons for excluding subjects from each of the populations listed above will be summarized by treatment group.

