#### **9.4.1.6 All-cause Mortality and Survival Time**

All-cause mortality rate with 95% CI at Day 14, Day 28 and overall by treatment group will be calculated as the proportion of subjects who experienced mortality regardless of the cause at or before Day 14 and Day 28, respectively. In this analysis, deaths occurring after EOS will not be used for analysis and any subject who does not have vital status information at Day 14 and 28 will not be included in the analysis. This analysis will be performed for both CR MITT and ITT Population.

In addition, for CR MITT Population, subgroup analysis regarding all-cause mortality at Day 28 will be performed. For the survival time up to End of Study (EOS), the survival curve using Kaplan-Meier method by treatment group will be presented. For the subjects whose vital status is survival at EOS, the subjects will be treated as right-censored at EOS. For the subjects whose vital status is not collected or unknown, the subjects will be treated as right-censored at last visit day.

All-cause mortality rate at Day 14, Day 28 and overall including death after EOS will be calculated by treatment group for ITT population.

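### The set labelled ITT requires a dose given after open-label allocation is known, so no mortality analysis covers all randomized patients; the effect is probably small and an all-randomized mortality table would settle it

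*SAP*

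**What the plan says.** SAP 5.1 defines ITT as "all randomized subjects who received at least 1 dose of the study treatment". Protocol 9.3 has the same definition: "All randomized patients who received at least 1 dose of the study treatment". SAP 4.1 states: "This is an open-label study".

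The other sets follow from this one. Micro-ITT is drawn from ITT (SAP 5.2), CR Micro-ITT from Micro-ITT (5.3), and CR-ME from CR Micro-ITT (5.4). The Safety population is equated with ITT, apart from being analysed by treatment received (5.5). CR Micro-ITT 2 (5.3.1) adds patients on local laboratory evidence. Its text does not repeat the dose requirement, and I read it as drawn from the same patients; it is not used for mortality.

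On Day 14, Day 28 and overall mortality, SAP 9.4.1.6 says: "This analysis will be performed for both CR MITT and ITT Population". It also says that "any subject who does not have vital status information at Day 14 and 28 will not be included in the analysis".

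The SAP foresees undosed patients. Section 6.6 provides that "Day 1 is the calendar day of randomization for subjects who did not take any IMP", and section 7.1 counts "Subjects who were randomized and treated" separately from those randomized. Section 7.1 also reports disposition for all randomized patients by arm, and the reasons for exclusion from each main population by arm.

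Protocol 7.13 says that, unless consent is withdrawn, "all randomized patients should be followed for the entire duration of the study".

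**The concern.** Under blinding, a dose requirement does limited harm, because a failure to start treatment can hardly depend on the arm. Here the site, and possibly the patient or family, know the allocation before the first dose. A decision not to start can therefore depend on it, and the patients concerned then leave every outcome analysis.

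Mortality is where this matters most. Clinical outcome is judged by an investigator who knows the arm (SAP 9.1.1), whereas death needs no such judgement. An all-randomized comparison would be the cleanest one available from this trial, and the plan does not include it. The rule on missing vital status can remove further patients from the same rates.

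There is also an internal tension. SAP 5.2 says that events after randomization should not remove a patient from Micro-ITT, yet Micro-ITT starts from a set whose entry condition is itself such an event.

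**Working it through.** **Inputs from the documents**
- About 150 patients randomized 2:1, with about 100 expected to be treated with cefiderocol (SAP 4.3).
- Phase 2 study: 452 randomized, 448 treated (Protocol 1.5.1). This is the only undosed rate in the documents.

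**Assumptions**
- Day 28 mortality of 30% or 20% among all randomized BAT patients. The documents state no mortality rate for planning.
- k undosed patients in the BAT arm, shown for several values of k. The number in this trial is not given.

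**Step 1: reproduce the plan's figure.** 150 × 2/3 = 100 cefiderocol and 150 × 1/3 = 50 BAT. The stated 100 is reproduced. It presumes that essentially everyone allocated is dosed.

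**Step 2: how many might be undosed.** (452 − 448)/452 = 4/452 = 0.9%.
- Expected number among 150: 150 × 4/452 = 1.3. Applying the exact 95% limits for the rate gives 0.4 to 3.4.
- Chance of at least one: 1 − (1 − 4/452)^150 = 74%.
- Expected number in the BAT arm: 50 × 4/452 = 0.4.

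**Step 3: effect on the BAT mortality rate.** Let d be the deaths among 50 randomized. If the k undosed patients all died, the rate as analysed is (d − k)/(50 − k). If they all survived, it is d/(50 − k).

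| Assumed mortality | k | All died | All survived | Shift in points |
|---|---|---|---|---|
| 30% (15/50) | 1 | 14/49 = 28.6% | 15/49 = 30.6% | -1.4 to +0.6 |
| 30% | 3 | 12/47 = 25.5% | 15/47 = 31.9% | -4.5 to +1.9 |
| 30% | 5 | 10/45 = 22.2% | 15/45 = 33.3% | -7.8 to +3.3 |
| 20% (10/50) | 1 | 9/49 = 18.4% | 10/49 = 20.4% | -1.6 to +0.4 |
| 20% | 3 | 7/47 = 14.9% | 10/47 = 21.3% | -5.1 to +1.3 |

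One undosed patient in the cefiderocol arm at 30% gives 29/99 = 29.3% or 30/99 = 30.3%, a shift of -0.7 to +0.3 points. That is half the BAT effect.

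**Step 4: scale.** The Clopper-Pearson 95% interval for 15/50 runs from 17.9% to 44.6%. One undosed BAT patient is small against that width. Three to five with the same outcome would be visible, but the Phase 2 rate does not suggest so many in one arm.

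**The case against.** The case against giving this much weight is strong, and most of it stands.

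- **Transparency.** A reader might infer that no analysis covers all randomized patients. That goes too far. SAP 7.1 tabulates disposition and exclusion reasons by arm, and SAP 8.1 lists major deviations for all randomized patients. An imbalance in undosed patients would be seen. Only their outcomes would be missing.
- **Direction.** A reader might infer that losses would fall mainly on BAT. Nothing in the documents supports this. BAT is the investigator's own choice of local standard of care (Protocol 5.2.2), and the regimen that would have been given outside the study is recorded for every patient at randomization (Protocol 5.4).
- **Size.** A shift of several points can be produced by placing 2 to 4 undosed patients in BAT and letting all of them die: 9/48 = 18.8% against 11/50 = 22.0%, or 9/46 = 19.6% against 13/50 = 26.0%. These are extreme cases. Their undosed rates of 4% and 8% compare with 0.9% in Phase 2, and they leave out the possibility that undosed patients survive.
- **Availability of vital status.** A reader might infer from Protocol 7.13 that vital status will be in hand for everyone. The sentence excepts those who withdraw consent. Vital status is entered at end of study (Protocol 7.8.1.1), which is timed from end of treatment (Protocol 8.5), and end of treatment presupposes a dose (Protocol Appendix 1, note c). An undosed patient has no defined end-of-study visit.
- **Consequence.** Mortality is a secondary endpoint reported as rates, intervals and survival curves. SAP 6.2 plans no test on it, so no error rate or success criterion is at risk.

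What remains is the definition itself. The set called ITT is a treated set, and mortality has no all-randomized analysis.

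**Conclusion.** The point holds as a modest weakness in the plan. Entry to the populations used for mortality depends on a dose given after allocation is known, and the plan foresees undosed patients without giving them an outcome analysis. No bias in a particular direction can be claimed.

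The likely size is about 1 patient in 150. Each undosed BAT patient moves BAT mortality by about -1.4 to +0.6 points at an assumed 30%, or -1.6 to +0.4 at 20%. This bears on a descriptive comparison whose intervals are far wider.

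The conclusion rests on three assumptions: the mortality rates above; the Phase 2 undosed rate, which comes from a different patient group and may not carry over to an open-label trial; and reading IMP in SAP 6.6 as study treatment in either arm, as SAP 8.2 does when it summarizes exposure by arm. A concentration of losses in the BAT arm would make the effect larger.

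**What to change.** - Add an all-randomized set, analysed by assigned arm, and report Day 14, Day 28 and overall all-cause mortality in it. For undosed patients, count days from randomization, as SAP 6.6 already provides. State a closing date for their overall mortality, since their end of study is otherwise undefined.
- For unknown vital status in this set, give best-case and worst-case bounds in place of dropping the patient.
- Relabel the current ITT set as treated or modified ITT. Tie Micro-ITT, CR Micro-ITT, CR-ME and Safety to the relabelled set so that their membership does not change. Redefining ITT outright would instead carry through to CR Micro-ITT, the primary efficacy population, and would break the cross-reference from Safety.
- Record the relabelling in SAP section 15, because it departs from the naming in Protocol 9.3.

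The cost is one extra table, some SAP wording, and obtaining Day 28 vital status for the few undosed patients who have not withdrawn consent. If everyone randomized was dosed, the new set coincides with the current one and the question is closed.

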### 5.2 Microbiological Intent-to-treat Population

The Microbiological Intent-to-treat (Micro-ITT) population includes all ITT subjects who have a baseline Gram-negative pathogen from an appropriate clinical specimen, regardless if the pathogen is carbapenem resistant or not. Subjects should not be excluded from this population based upon events that occurred postrandomization (e.g., lost to follow-up).

### 5.3 Carbapenem-resistant Microbiological Intent-to treat Population

The Carbapenem-resistant Microbiological Intent-to-treat (CR Micro-ITT) population includes all Micro-ITT subjects whose at least 1 of the baseline Gram-negative pathogens is carbapenem resistant and the carbapenem-resistant pathogen is confirmed by central laboratory. Subjects with *Stenotrophomonas maltophilia* as baseline pathogen will also be included in this population. If subsequent central laboratory results confirm that the pathogen is not carbapenem resistant, the subject with the pathogen will not be included in this population.

### **5.3.1 Carbapenem-resistant Microbiological Intent-to-treat 2 Population**

The Carbapenem-resistant Microbiological Intent-to-treat 2 (CR Micro-ITT 2) population includes all subjects in the CR Micro-ITT population. In addition, this CR Micro-ITT 2 population will include subjects whose at least 1 of the baseline Gram-negative pathogens is carbapenem resistant confirmed by local laboratory if there is no central laboratory data available.

### **5.4 Carbapenem-resistant Microbiologically Evaluable Population**

The Carbapenem-resistant Microbiologically Evaluable (CR-ME) population includes all CR Micro-ITT subjects who follow important components of the study as specified in the protocol with no major protocol violations.

Criteria for inclusion are:

- $\geq 5$  days of intravenous study treatment unless treatment was a failure
- Underwent TOC assessment
- Subjects without any major protocol inclusion or exclusion violations
- Subjects with no violations of restrictions for concomitant therapy, including concomitant antibiotics effective against Gram-negative bacteria

Details will be specified in protocol deviation specification.

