2.2	03 Dec 2018	[REDACTED]	

▪ Change the wording from sensitivity to supplementary per ICH E9 R1

▪ Clarify the interim analysis for DSMB

▪ Exclude neomycin oral administration from additional antibiotics (section 6.8).

▪ Clarify Composite of Survival and No Change in Antibiotic Treatment will be determined by Shinogi internally rather than EDC data (section 9.4.1.9).

▪ Exclude PTT from LAB analysis (section 10.2)

▪ Minor update of wording

2.3	12 Feb 2019	[REDACTED]	

▪ Specify medical monitor will adjudicate additional antibiotics based on available data, and delete sentences about neomycin oral administration.

2.4	11 Apr 2019	[REDACTED]	

▪ Delete signature page to use Veeva Vault eSignature due to change TMF management plan.

▪ Terminology change from microbiological

			
eradication/failure to eradication/persistence. (Section 9.1.6, 9.1.7, 9.2.6)
 

▪ Change terminology from protocol deviation list to protocol deviation specification. Also clarify criteria for ME population is specified in the document. (section 5.4 and 8.1)

▪ Change the definition of new/super infection to new pathogen on or after Day 3 by the input from medical group. (section 9.1.5)

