#### **6.4.2 Missing Microbiological or Clinical Outcome**

For clinical and microbiological outcomes, subjects who are lost to follow-up or have missing or "indeterminate" outcomes will be included in the denominator as indeterminate for cure/eradication rate, i.e., considered as not responders. If judged by the investigator that a subject died due to pneumonia, BSI/sepsis or cUTI, the clinical outcome will be considered as clinical failure after the event of death. If a subject died due to other reasons, the clinical outcome will be considered as "indeterminate" after death.

For clinical outcome, if a subject received additional antibiotics for target disease (i.e., baseline infection) before the target date, the outcome will be considered as "clinical failure". If a subject did not receive additional antibiotics for target disease before the target date, the outcome will be considered as "indeterminate".

Missing values for other individual data points will remain as missing unless otherwise specified. All analysis will be based on observed case unless otherwise stated.

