## 9.1 Efficacy Assessment

### 9.1.1 Clinical Outcomes for EOT and TOC

The clinical outcomes will be assessed by the investigator according to the following criteria established for each infection site at EOT and TOC. In case treatment duration is extended beyond 14 days, an additional clinical outcome will be assessed on Day 14. The clinical outcomes will be entered in the electronic case report form (eCRF).

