#### 9.1.1.1 HABP/VABP/HCABP

- **Clinical Cure:** Resolution or substantial improvement of baseline signs and symptoms of pneumonia including a reduction in SOFA score and clinical pulmonary infection score (CPIS), and improvement or lack of progression of chest radiographic abnormalities such that no antibacterial therapy is required for the treatment of the current infection.
- **Clinical Failure:** No apparent response to therapy; persistence or worsening of baseline signs and/or symptoms of pneumonia; reappearance of signs and/or symptoms of pneumonia; development of new signs and/or symptoms of pneumonia requiring antibiotic therapy other than, or in addition to, study treatment therapy; progression of chest radiographic abnormalities; or death due to pneumonia.
- **Indeterminate:** Lost to follow-up such that a determination of clinical cure/failure cannot be made.

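### The CR-ME criterion requiring a TOC assessment has no failure exception; read literally, it drops patients who die before TOC and raises each arm's supplementary TOC response rate by 1/(1 − d)

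*SAP*

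**What the plan says.** **Membership.** SAP 5.4 forms CR-ME from CR Micro-ITT by four criteria, and Protocol 9.3 lists the same four. The first asks for at least 5 "days of intravenous study treatment unless treatment was a failure". The second is "Underwent TOC assessment", with no exception. SAP 5.4 then adds: "Details will be specified in protocol deviation specification". The version 2.4 entry in the SAP's Records on Revisions says: "Also clarify criteria for ME population is specified in the document". That specification is not among the documents.

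**Outcome after death.** SAP 6.4.2, whose heading concerns missing outcomes, says that when the investigator attributes a death to the infection, "the clinical outcome will be considered as clinical failure after the event of death". A death from another cause is indeterminate, and patients with missing or indeterminate outcomes "will be included in the denominator as indeterminate for cure/eradication rate, i.e., considered as not responders".

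**Outcome definitions.** SAP 9.1.1 says: "The clinical outcomes will be assessed by the investigator according to the following criteria established for each infection site at EOT and TOC". The pneumonia failure definition ends with "progression of chest radiographic abnormalities; or death due to pneumonia", and the cUTI and BSI/sepsis definitions end in the matching way. The cUTI microbiological definition (SAP 9.1.3.2) does not mention death; with no urine culture the outcome is indeterminate.

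**Use.** Protocol 9.9 uses CR-ME to check robustness, and SAP section 9 calls it supplementary. It appears in SAP 9.3.2.1, in 9.3.2.2 (the alternative cUTI threshold), and in the tables of 9.4.1.1 and 9.4.1.2.

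**The concern.** The two criteria work against each other. A patient who dies of the infection on Day 4 is admitted by the first, as a treatment failure, and removed by the second, because the TOC visit (EOT + 7 days, ± 2) never took place. Yet that patient's TOC result is known: SAP 6.4.2 makes it a failure. A death from another cause before TOC is likewise a non-response under that section, and the literal criterion removes it too.

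The exclusion therefore depends on outcome. At TOC it removes only non-responders, so the cures stay and the denominator shrinks. A robustness set built this way can look reassuring because known failures have left it. Living failures are a smaller matter, since Protocol 7.13 asks sites to follow them through TOC where possible.

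**Working it through.** **Inputs.** The one design figure to reproduce is the allocation: 150 × 2/3 = 100 treated with S-649266, as Protocol 9.2 states. It does not bear on the claim. The documents give no expected cure rate for this trial and no share dying before TOC, so every rate below is an assumption.

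**Formula.** In one arm, let N be the patients who meet all the other CR-ME criteria, C the responders at TOC, and D those who die before TOC. All D are non-responders (SAP 6.4.2).

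- Deaths kept: C/N.
- Deaths dropped: C/(N − D).
- Ratio: N/(N − D) = 1/(1 − d), with d = D/N.

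| d | 1/(1 − d) | 50% becomes | 60% becomes |
|---|---|---|---|
| 5% | 1.053 | 52.6% | 63.2% |
| 10% | 1.111 | 55.6% | 66.7% |
| 15% | 1.176 | 58.8% | 70.6% |
| 20% | 1.250 | 62.5% | 75.0% |
| 25% | 1.333 | 66.7% | 80.0% |

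**Counts.** About half of 150 patients are to have pneumonia: 75, or 50 and 25 at 2:1. Suppose, as an upper limit, that all 25 BAT patients would otherwise be in CR-ME, with 12 cures and 3 deaths before TOC. Clopper-Pearson intervals, the SAP's method:

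- Kept: 12/25 = 48.0% (95% CI 27.8 to 68.7).
- Dropped: 12/22 = 54.5% (95% CI 32.2 to 75.6).
- Check: 1/(1 − 3/25) = 1.136, and 48.0% × 1.136 = 54.5%.

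**cUTI.** The primary endpoint there is microbiological. A patient who dies before TOC without a TOC culture is indeterminate (9.1.3.2), hence a non-responder (6.4.2), so the same factor applies.

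**EOT is different.** The CR-ME tables in 9.4.1.1 and 9.4.1.2 also report EOT. A patient cured at EOT who dies before TOC is an EOT responder, and dropping that patient removes a success. With 14/25 = 56.0% cured at EOT, and three of those 14 dying before TOC, the rate becomes 11/22 = 50.0%. The factor would have given 56.0%/(1 − 0.12) = 63.6%. The EOT rate can fall, so the formula must not be used there.

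**The case against.** **The operative rule may lie elsewhere.** SAP 5.4 defers to the deviation specification, and the revision record says that the criteria are set out there. It may already contain an exception. The visible text also allows a benign reading: SAP 9.1.1 lists death from the infection as a failure at EOT and TOC, so such a death could count as assessed. Under either, the effect is zero for the deaths covered. This stands as uncertainty but does not settle the text. SAP 6.4.2 assigns the outcome by rule under a missing-outcome heading; no passage says that an assigned outcome amounts to having undergone the assessment; and the cUTI microbiological definition has no death element.

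**Death is well covered elsewhere.** This is true. CR Micro-ITT is primary and keeps these patients as non-responders. The supplementary clinical definitions (SAP 9.2.2) count any death from Day 4 as failure, and mortality is tabulated in CR Micro-ITT and ITT. But SAP 9.4.1.3 applies the 9.2.2 definitions to CR Micro-ITT and Micro-ITT only, so they do not repair CR-ME.

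**Stronger readings that the documents do not support.**

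- A reader might infer a biased treatment comparison. None is planned in CR-ME: the SAP gives rates and intervals by arm, and its only between-arm comparison is the composite in 9.4.1.9, in CR Micro-ITT. Nor is the direction fixed. If someone compared the arms informally, unequal shares could matter: equal 50% rates with 20% and 10% dropped would read 62.5% and 55.6%. But with 25% and 15% dropped, 20% against 60% (−40.0 points) becomes 26.7% against 70.6% (−43.9), so the arm losing more deaths does not always gain on the difference scale.
- A reader might take 1/(1 − d) as the ratio of the CR-ME rate to the CR Micro-ITT rate. It is not. The other criteria also remove patients, and not obviously at random: patients with Gram-negative-active antibiotic violations are excluded, while SAP 6.4.2 links additional antibiotics for the baseline infection to clinical failure.

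**Conclusion.** The concern holds as a gap in a supplementary definition. As written, the TOC criterion drops patients who die before TOC and multiplies each arm's CR-ME TOC response rate by 1/(1 − d), relative to the same set with them kept. The factor is exact for TOC; its size depends on an unknown d. For an assumed d of 5% to 15%, a 50% rate rises by 2.6 to 8.8 points. In the small-arm example the shift is 6.5 points, inside intervals more than 40 points wide.

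The conclusion rests on the literal reading and on an unseen specification that adds no exception. It reaches only descriptive CR-ME tables, on which no test, difference or ratio is planned. The CR Micro-ITT primary analysis and the mortality tables are unaffected. Severity is minor to should-fix: a cheap improvement to a robustness check.

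**What to change.** In SAP 5.4, replace the second criterion with:

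*Underwent TOC assessment, or died from any cause before TOC, or was a clinical failure before TOC with no TOC assessment available. Such patients are kept as non-responders at TOC. An observed TOC result, including a TOC urine culture, is never overridden. Outcomes observed at EOT are kept as observed.*

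Record the change in SAP section 15 and match it in the deviation specification. In the SAP 7.1 table of exclusion reasons, show any remaining exclusions for no TOC assessment by arm.

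- Death from any cause is used so that this criterion does not turn on a cause-of-death judgement in an open-label trial. For deaths with fewer than 5 days of treatment, the first criterion still depends on whether treatment was a failure.
- The clause protecting observed results is needed because the primary definitions (9.1.1, 9.1.3), unlike the supplementary ones (9.2.2), do not carry an EOT failure forward to TOC.

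Cost: the replacement wording in 5.4, one line in section 15, a matching line in the specification, and one row in a table already planned. No protocol amendment is needed, since Protocol 9.1 lets the SAP record deviations. The downside is that CR-ME TOC rates become slightly less favourable. If the specification already contains the exception, the change only makes the SAP say so.
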